19.1.1. ALL TEAEs

Incidence of TEAEs will be presented by System Organ Class and Preferred Term and also analyzed by relationship to study drug, seriousness, severity, and maximum severity. Summaries by SOC and PT will present SOC in alphabetical order and PT within the SOC in descending order of incidence in the total teduglutide treatment arm.

19.1.1.1. Severity

Severity is classified as mild/moderate/severe. TEAEs with a missing severity will be classified as severe. If a subject reports a TEAE more than once within that SOC / PT, summaries by severity will only provide the highest severity classification of the subject for the corresponding incidence summaries by SOC / PT.

The events that are graded according to CTCAE criteria will be indicated in the listings.

19.1.1.2. Relationship to Study Drug

Relationship, as indicated by the Investigator, is classed as “*not related*” or “*related*”. A “*related*” TEAE is defined as a TEAE with a relationship of “*related*” to study drug. TEAEs with a missing relationship to study drug will be regarded as “*related*” to study drug. AE

Document: \\quintiles.net\Enterprise\Apps\sasdata\SASa\sas\Shire\Teduglutide\Biostatistics\Documentation\SAP\TE
D-C14-006_SAP_Final_V1.0_20170714

Author: **PPD** Version Number: Final V1.0
Version Date: 14Jul2017

Template No: CS_TP_BS016 – Revision 3
Effective Date: 01May2012

Reference: CS_WI_BS005

Copyright © 2012 Quintiles Transnational Corp. All rights reserved.

The contents of this document are confidential and proprietary to Quintiles Transnational Corp. Unauthorized use, disclosure or reproduction is strictly prohibited.

summaries by relationship will exclude the standard of care treatment arm.

19.1.2. SERIOUS ADVERSE EVENTS

Serious adverse events (SAEs) are those events recorded as “Serious” on the Adverse Events Form of the eCRF. Any SAE that occurs from the time of the signing of the ICF through last study visit (week 28 or EOS) will be captured. A summary of TESAEs by SOC and PT will be prepared, as well as summaries by event and causal relationship to study drugs. A listing of SAEs will be presented.

19.1.3. AEs LEADING TO DISCONTINUATION OF STUDY DRUG

AEs leading to permanent discontinuation of study drug will be identified by the “Study drug discontinued” response for action taken with study treatment in the Adverse Events Form of the eCRF.

Separate listings will be provided for AEs leading to permanent discontinuation of study drug.

19.1.4. ADVERSE EVENTS LEADING TO DEATH

AEs leading to Death are those events which are recorded as “Fatal” on the Adverse Events Form of the eCRF. A listing of AEs leading to death will be presented.

19.2. LABORATORY EVALUATIONS

Laboratory evaluations that are done at study site visits will be collected and processed via a central laboratory (Covance), including panels for Hematology, Clinical Chemistry, Coagulation and Urinalysis. The central laboratory data will be transferred to Quintiles for analyses. Laboratory evaluations that are required at intervals that do not coincide with study site visits may be obtained by a local laboratory. The local laboratory data will be collected on the local laboratory tests form of eCRF. Laboratory evaluations to be included in the tables or listings are presented in the lab test table ([Table B](#)) below.

Document:	\\quintiles.net\Enterprise\Apps\sasdata\SASa\sas\Shire\Teduglutide\Biostatistics\Documentation\SAP\TE D-C14-006_SAP_Final_V1.0_20170714		
Author:	PPD	Version Number:	Final V1.0
		Version Date:	14Jul2017

Template No: CS_TP_BS016 – Revision 3
Effective Date: 01May2012

Reference: CS_WI_BS005

Copyright © 2012 Quintiles Transnational Corp. All rights reserved.

The contents of this document are confidential and proprietary to Quintiles Transnational Corp. Unauthorized use, disclosure or reproduction is strictly prohibited.

Table B Laboratory Tests

Hematology	Chemistry	Coagulation	Urinalysis
Hemoglobin	Albumin	Prothrombin Time	Ur Blood*
Hematocrit	Alkaline Phosphatase	Prothrombin Intl. Normalized Ratio (INR)	Ur Glucose*
Platelets	Alanine Aminotransferase (ALT)		Ur Microscopic*
Erythrocytes	Aspartate Aminotransferase (AST)		Ur PH
RBC Morphology*	Amylase		Ur Osmolality
Leukocytes	Lipase		Ur Protein
Neutrophils	Bicarbonate		Ur Sodium
Lymphocytes	Bilirubin		Ur Specific Gravity
Monocytes	Direct Bilirubin		
Eosinophils	Indirect Bilirubin		
Basophils	Blood Urea Nitrogen		
Neutrophils/Leukocytes	Calcium		
Lymphocytes/Leukocytes	Chloride		
Monocytes/Leukocytes	Cholesterol		
Eosinophils/Leukocytes	Creatinine		
Basophils/Leukocytes	C Reactive Protein		
	Glomerular Filtration Rate (GFR)		
	Glucose		
	Gamma Glutamyl Transferase (GGT)		
	Lipase		
	Magnesium		
	Phosphorus		
	Potassium		
	Sodium		
	Triglycerides		
	Uric Acid		

Note: * lab tests with categorical results.

Lab data will be presented in SI units. The summaries will be based on central lab results only.

Quantitative laboratory measurements reported as “< X”, i.e. below the lower limit of quantification (BLQ), or “> X”, i.e. above the upper limit of quantification (ULQ), will be converted to X for the purpose of quantitative summaries, but will be presented as recorded, i.e. as “< X” or “> X” in the listings.

The following summaries will be provided for hematology, clinical chemistry and selected urinalysis laboratory data with quantitative results:

Document:	\\quintiles.net\Enterprise\Apps\sasdata\SASa\sas\Shire\Teduglutide\Biostatistics\Documentation\SAP\TE D-C14-006_SAP_Final_V1.0_20170714		
Author:	PPD	Version Number:	Final V1.0
		Version Date:	14Jul2017

Template No: CS_TP_BS016 – Revision 3
Effective Date: 01May2012

Reference: CS_WI_BS005

Copyright © 2012 Quintiles Transnational Corp. All rights reserved.

The contents of this document are confidential and proprietary to Quintiles Transnational Corp. Unauthorized use, disclosure or reproduction is strictly prohibited.

- Actual and change from baseline by scheduled site visit
- Shift from baseline according to normal range criteria at each scheduled post-baseline site visit
- Incidence of markedly abnormal values according to criteria defined in section Appendix 3
- Listing of subjects meeting markedly abnormal criteria

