Treatment of both pediatric and adult patients is focused on achieving adequate intestinal absorption to allow for minimization or discontinuation of PN/IV support. Because children are at higher risk for intestinal failure-associated liver disease, reducing PN support is far more urgent in this population. About 30% of infants who develop SBS during the neonatal period become independent of PN/IV requirements by 12 months of age, and an additional 10% wean off PN/IV support by 24 months of age. After this time, intestinal adaptation and growth occurs much more slowly, and many children remain terminally dependent on PN/IV support. Due to the risks of intestinal failure-associated liver disease, catheter-related blood stream infections, central line-associated venous thrombosis and dwindling central venous access, achieving autonomy from parenteral support remains an urgent goal for all affected children (Khan et al, 2015; Squires et al, 2012).

This study proposes to investigate the safe and appropriate use of teduglutide in the pediatric population for up to 24 weeks for the purpose of providing longer-term data in regard to safety and potential to explore further efficacy including PN reduction and ability to completely wean off parenteral support. This protocol was developed with input from expert advisors from intestinal rehabilitation centers who offered advice on the most appropriate use of teduglutide in pediatric patients. The aim of teduglutide treatment is to increase absorptive capacity in order to yield decreases in parenteral support. The experts anticipated that there would be several direct benefits from decreased parenteral support, including less exposure to PN/IV

constituents, less central line manipulation with lower risk of infection, and more time to focus on oral rehabilitation strategies.

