15. Subjects with active Crohn's disease who had been treated with biological therapy (eg, antitumor necrosis factor [anti-TNF]) within the 6 months prior to the screening visit
16. Subjects with inflammatory bowel disease (IBD) who required chronic systemic immunosuppressant therapy that had been introduced or changed during the 3 months prior to screening
17. More than 3 SBS-related or PN-related hospital admissions (eg, documented infection-related catheter sepsis, clots, bowel obstruction, severe water-electrolyte disturbances) within 3 months prior to the screening visit
18. Any major unscheduled hospital admission which affects parenteral support requirements within 1 month prior to or during screening, excluding uncomplicated treatment of bacteremia, central line replacement/repair, or issues of similar magnitude in an otherwise stable subject
19. Body weight < 10 kg at the screening and randomization visits
20. Signs of active severe or unstable, clinically significant hepatic impairment shown by any of the below laboratory test results during the screening period:
 - a. Total bilirubin ≥ 2 x upper limit of normal (ULN)
 - b. Aspartate aminotransferase (AST) ≥ 7 x ULN
 - c. Alanine aminotransferase (ALT) ≥ 7 x ULNFor subjects with Gilbert's disease:
 - d. Indirect (unconjugated) bilirubin ≥ 2 x ULN

21. Signs of known continuous active or unstable, clinically significant renal dysfunction shown by results of an estimated glomerular filtration rate (eGFR) below 50 mL/min/1.73 m².
22. Parent(s) and/or subjects who are not capable of understanding or not willing to adhere to the study visit schedule and other protocol requirements
23. Unstable, clinically significant active, untreated pancreatic or biliary disease
24. Any condition, disease, illness, or circumstance that in the investigator’s opinion puts the subject at any undue risk, prevents completion of the study, or interferes with analysis of the study results. Examples of potential disease states/illnesses that may be excluded are listed in the table below.

Table 4-1 Excluded Diseases and Illnesses

Body system	Known conditions excluded
Related to SBS	
 • Ongoing radiation enteritis • Untreated celiac disease • Refractory or tropical sprue • Pseudo-obstruction

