6.1.4 Dose Interruption of Individual Subjects

Teduglutide administration for an individual subject may need to be stopped if the subject has an adverse event of special interest (see risks in table below) that is severe in intensity [Grade 3 or higher as defined by the National Cancer Institute’s Common Terminology Criteria for Adverse Events (CTCAE)]. This may occur if an event is attributable to study drug or a subject experiences an unexplained CTCAE Grade 3 or higher that is not reasonably related to the underlying disease process. The determination of length of the discontinuation, temporary or permanent, depends on the clinical situation.

Investigators and the DSMB should be guided by the descriptions of Grade 3 and 4 events below, as they relate to identified risks associated with the administration of teduglutide.

Identified Risk	Grade 3 Description	Grade 4 Description
Gastrointestinal Disorders		
Colorectal polyps	Severe or medically significant but not immediately life threatening; hospitalization or prolongation of existing hospitalization indicated; disabling; limiting self-care activities of daily living	Life-threatening consequences; urgent intervention indicated
Intestinal Obstruction	Hospitalization indicated; elective operative intervention indicated; limiting self-care activities of daily living; disabling	Life-threatening consequences; urgent operative intervention indicated
Gallbladder and Bile Duct Disease		
Cholecystitis	Severe symptoms; radiologic, endoscopic or elective operative intervention indicated	Life-threatening consequences; urgent operative intervention indicated
Gallbladder perforation	Not Applicable	Life-threatening consequences; urgent intervention indicated
Gallbladder obstruction	Symptomatic and severely altered gastrointestinal function; tube feeding, total parenteral nutrition or hospitalization indicated; nonemergent operative intervention indicated	Life-threatening consequences; urgent operative intervention indicated

Identified Risk	Grade 3 Description	Grade 4 Description
Gallbladder infection	Intravenous antibiotic, antifungal, or antiviral intervention indicated; radiologic, endoscopic, or operative intervention indicated	Life-threatening consequences; urgent intervention indicated
Alkaline Phosphatase increased	> 5.0 to 20.0 x Upper limit of normal	> 20.0 x Upper limit of normal
Blood bilirubin increased	> 3.0 to 10.0 x Upper limit of normal	> 10.0 x Upper limit of normal

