19.2.1. LABORATORY REFERENCE RANGES AND MARKEDLY ABNORMAL CRITERIA

Quantitative laboratory measurements will be compared with the relevant laboratory reference ranges in SI units and categorized as:

- Low: Below the lower limit of the laboratory reference range.
- Normal: Within the laboratory reference range (upper and lower limit inclusive).
- High: Above the upper limit of the laboratory reference range.

In addition to the high and low quantitative laboratory assignments (as identified by means of the laboratory reference ranges), markedly abnormal quantitative safety (and other) laboratory assessments will also be identified in accordance with the predefined markedly abnormal criteria as presented in [Appendix 3](#).

The number and percentage of subjects whose post-baseline results qualifying as markedly abnormal will be summarized by treatment group and the parameter. A listing will present all values for a subject and laboratory parameter if at least one post-baseline value for that subject and parameter is markedly abnormal.

Laboratory results will also be included in appendix data listings for each lab panel (chemistry, hematology, coagulation and urinalysis) by treatment, subject, visit and parameter. Values outside the normal range will be flagged. Local lab test results will only be presented in appendix data listings. Categorical test results, coagulation and pregnancy results (B-hCG, Qualitative and B-hCG, Quantitative) also will only be included in data listings.

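### A child whose liver tests are already raised at baseline can worsen to 8 x ULN (ALT/AST) or 3 x ULN (total bilirubin) without being counted in any categorical laboratory table.

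*SAP*

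**What the plan says.** SAP 19.2 lists four outputs for quantitative chemistry: actual values and change by site visit, a shift table, the incidence of markedly abnormal values, and a listing of the children who meet those criteria. The shift table is "Shift from baseline according to normal range criteria at each scheduled post-baseline site visit". SAP 19.2.1 gives it three categories, of which the top one is "High: Above the upper limit of the laboratory reference range", with no grades above that.

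For the incidence table, "The number and percentage of subjects whose post-baseline results qualifying as markedly abnormal will be summarized by treatment group and the parameter". Appendix 3 supplies the limits:

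- ALT and AST: above 8 x ULN
- total bilirubin: above 3 x ULN
- alkaline phosphatase: above 5 x ULN
- direct bilirubin: above 34.208 umol/L

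GGT and indirect bilirubin are in SAP Table B but have no row in Appendix 3. Summaries use central-laboratory results only; local results are listed.

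Protocol 4.3, exclusion 20, bars children with "Signs of active severe or unstable, clinically significant hepatic impairment shown by any of the below laboratory test results during the screening period". Its limits are "Aspartate aminotransferase (AST) ≥ 7 x ULN", the same multiple for ALT, and total bilirubin at or above 2 x ULN. Protocol 6.1.4 lists increased bilirubin among the drug's identified risks and puts Grade 3 at "> 3.0 to 10.0 x Upper limit of normal".

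**The concern.** The protocol gives liver disease as a reason for the trial: "Because children are at higher risk for intestinal failure-associated liver disease, reducing PN support is far more urgent in this population". Exclusion 20 removes only the most abnormal liver tests, so children with ALT or AST between 1 and 7 x ULN, or total bilirubin between 1 and 2 x ULN, may enrol. Raised baseline values are foreseeable in children dependent on parenteral nutrition.

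For such a child the shift table stops being informative. The child starts in the top category and stays there however far the value climbs. The only other categorical table starts well above the entry limits. Nothing planned counts, by dose group, how many children moved from mildly raised to a level that would have barred them at entry, or in how many ALT or AST and bilirubin rose together. The study makes no claims of significance (SAP 7.5), so counts by group are the main form its safety evidence will take.

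**Working it through.** No sample size or error rate is involved. The check applies the documents' own limits to pairs of baseline and post-baseline values, in multiples of ULN.

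**Rules**
- Shift category: High if the value exceeds 1 x ULN, otherwise Normal in these examples (SAP 19.2.1).
- Markedly abnormal: ALT or AST > 8, total bilirubin > 3 (SAP Appendix 3).
- Exclusion 20 level: ALT or AST ≥ 7, total bilirubin ≥ 2 (Protocol 4.3).
- Counted as a case: shift is Normal to High, or the value is markedly abnormal.

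| Test | Baseline | Post-baseline | Shift | Markedly abnormal | Exclusion 20 level | Counted |
|---|---|---|---|---|---|---|
| ALT or AST | 1.5 | 6.9 | High to High | no | no | no |
| ALT or AST | 1.5 | 7.5 | High to High | no | yes | **no** |
| ALT or AST | 1.5 | 8.0 | High to High | no | yes | **no** |
| ALT or AST | 1.5 | 8.1 | High to High | yes | yes | yes |
| ALT or AST | 0.8 | 7.5 | Normal to High | no | yes | yes |
| Total bilirubin | 1.5 | 1.9 | High to High | no | no | no |
| Total bilirubin | 1.5 | 2.0 | High to High | no | yes | **no** |
| Total bilirubin | 1.5 | 3.0 | High to High | no | yes | **no** |
| Total bilirubin | 1.5 | 3.1 | High to High | yes | yes | yes |
| Total bilirubin | 0.8 | 2.5 | Normal to High | no | yes | yes |

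**Width of the uncounted range for a child already High**
- ALT or AST: 1 to 8 x ULN, a width of 8 − 1 = 7 multiples. The part at exclusion 20 level is 8 − 7 = 1 multiple.
- Total bilirubin: 1 to 3 x ULN, a width of 3 − 1 = 2 multiples. The part at exclusion 20 level is 3 − 2 = 1 multiple.
- GGT: no upper bound, because Appendix 3 has no row for it. Indirect bilirubin is in the same position.

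These are widths of the scale, not shares of children.

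**Direct bilirubin.** Its separate limit can catch part of the bilirubin band. Direct cannot exceed total, so with total at or below 3 x ULN the flag can fire only if 3 x ULN > 34.208, that is, a total-bilirubin ULN above 34.208 / 3 = 11.4 umol/L. To fire at a total of 2 x ULN it needs a ULN above 34.208 / 2 = 17.1 umol/L. The documents give no ULN. At 11.4 or below the flag adds nothing in the 2 to 3 x band. Above 17.1 it can act across the whole band, depending on how much of the bilirubin is direct.

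**Weight of one child.** Protocol 4.1 plans at least 10 children per dose group and up to 8 in standard of care: 1/10 = 10 percentage points, and 1/8 = 12.5.

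**The case against.** The best case for the plan as it stands has five parts.

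- **Adverse events.** Protocol 6.1.1.2 and 6.1.6 require laboratory changes judged clinically significant to be reported as adverse events, and SAP 19.1 tabulates those by arm and dose group. This stands, and it is why the gap is not one of all capture. It does depend on each investigator's judgement, and 6.1.6 gives abnormalities tied to the disease and present at baseline as its example of results that need not be significant.
- **The benchmark.** Exclusion 20 is an entry criterion. For bilirubin and alkaline phosphatase, Appendix 3 starts exactly where Grade 3 starts in Protocol 6.1.4. This also stands. A reader might infer that the SAP limits contradict the protocol or are wrong; the documents do not support that. The 6.1.4 table has no ALT or AST row, so for those two tests exclusion 20 is the only limit the supplied protocol offers.
- **Severe cases are counted.** A reader might infer that a child with severely raised values appears in no table. That is not so: anything above the Appendix 3 limits is counted and listed whatever the baseline, and a child with normal baseline values appears as Normal to High.
- **Data remain visible.** By-visit maxima, flagged listings and DSMB review about every 3 months all exist, and with some 20 treated children the listings can be read directly. But maxima do not count children, and an already-high child is flagged at every visit, so the flag does not mark worsening.
- **Unseen material.** The table shells are in a separate file, so a graded table there cannot be ruled out. The SAP text does not call for one.

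**Conclusion.** The point holds as a specific gap in counting. For a child already above ULN at baseline, worsening up to and including 8 x ULN (ALT or AST) or 3 x ULN (total bilirubin) is counted in no categorical laboratory table in SAP 19.2, and a further rise in a raised GGT is never counted. The part that also meets exclusion 20 is narrower: 7 to 8 x for ALT or AST and 2 to 3 x for total bilirubin. How many children will fall there cannot be known from the documents.

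It would go too far to conclude that a liver signal would be missed, since adverse events, listings and summary values remain.

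Two assumptions matter. Exclusion 20 is read from a protocol that runs to Amendment 2, while SAP section 2 cites Amendment 4, so the entry limits then in force cannot be confirmed. And a crossing is best called new relative to the SAP baseline, because a value can change between the screening result and that baseline. The High-to-High problem depends on neither.

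**What to change.** In SAP 19.2.1, add one table by dose group, total teduglutide and standard of care, from central-laboratory results, for ALT, AST, alkaline phosphatase, GGT and total bilirubin. It should show:

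1. The shift from baseline to the worst post-baseline value in multiples of ULN. Possible bands are ≤1, >1 to 3, >3 to 5, >5 to <7, 7 to 8 and >8 for ALT and AST; ≤1, >1 to <2, 2 to 3 and >3 for total bilirubin; ≤1, >1 to 3, >3 to 5 and >5 for alkaline phosphatase and GGT. Cut points that are not in the documents are display choices only.
2. The number and percentage of children below the exclusion 20 limits at the SAP baseline who later reach or exceed them, using the limits in the protocol amendment the SAP follows.
3. The number with ALT or AST and total bilirubin both raised at the same visit.

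Leave Appendix 3 and all eligibility, dosing and stopping rules unchanged.

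The cost is a few lines of SAP text and one table, with no new data. More children will be shown with liver test increases, some of them reflecting the underlying disease, so the standard of care column should sit alongside. A peak seen only in a local laboratory would still be missed; a footnote should say so.

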19.2.1. LABORATORY REFERENCE RANGES AND MARKEDLY ABNORMAL CRITERIA

Quantitative laboratory measurements will be compared with the relevant laboratory reference ranges in SI units and categorized as:

- Low: Below the lower limit of the laboratory reference range.
- Normal: Within the laboratory reference range (upper and lower limit inclusive).
- High: Above the upper limit of the laboratory reference range.

In addition to the high and low quantitative laboratory assignments (as identified by means of the laboratory reference ranges), markedly abnormal quantitative safety (and other) laboratory assessments will also be identified in accordance with the predefined markedly abnormal criteria as presented in [Appendix 3](#).

The number and percentage of subjects whose post-baseline results qualifying as markedly abnormal will be summarized by treatment group and the parameter. A listing will present all values for a subject and laboratory parameter if at least one post-baseline value for that subject and parameter is markedly abnormal.

Laboratory results will also be included in appendix data listings for each lab panel (chemistry, hematology, coagulation and urinalysis) by treatment, subject, visit and parameter. Values outside the normal range will be flagged. Local lab test results will only be presented in appendix data listings. Categorical test results, coagulation and pregnancy results (B-hCG, Qualitative and B-hCG, Quantitative) also will only be included in data listings.

